Y_{Post} – The outcome variable of interest, either: 1) times having sex without condoms in the past 3 months (continuous; values range 0 to k , where 0= has had sex without condoms 0 times in past 3 months, and k = number of times having sex without condoms in past 3 months); or 2) number of sexual partners in the past 3 months (continuous; values range 0 to k , where 0= has 0 sexual partners in past 3 months, and k = number of sexual partners in past 3 months) reported by participant i at the 9-month follow-up. (see Table 1 for full details on the variable construction).

Y_{Pre} – The baseline measure of the outcome variable of interest reported by participant i at baseline (see Table 2 for full details on the variable construction); variable will be re-centered at the grand mean for analysis.

³⁹ With the assumption that we maintain low attrition and differential attrition and that the study otherwise executes the RCT with integrity, we should be able to estimate an un-biased estimate of the average treatment effect of the intent to treat participants with *PS-R* by comparing differences in the means of the outcome variable reported by the treatment group with those reported by the control group. We could then provide a compelling response to our research question by testing the hypothesis that there is no difference between the two groups using straight-forward hypothesis testing statistics (t-test). With that said, we propose a regression-based model that includes covariates, because randomization should ensure covariates are uncorrelated with the treatment variable (i.e., they should not affect the estimate of the treatment effect), and in the instance they are significant predictors of the outcome, their inclusion in a regression model will decrease the standard error of the estimates, making them more precise. See: Angrist, J. D., & Pischke, J. (2009). Mostly harmless econometrics: An empiricist's companion. Princeton: Princeton University Press; Rosenblum, M. and van der Laan, M. J. (2009), Using Regression Models to Analyze Randomized Trials: Asymptotically Valid Hypothesis Tests Despite Incorrectly Specified Models. *Biometrics*, 65: 937-945. doi:10.1111/j.1541-0420.2008.01177.x.

⁴⁰ As part of our sensitivity analyses, we will construct a logistic regression model to explore any potential differences in our effect estimates given the model utilized.

T – A dummy treatment indicator variable whose value equals 1 if the participant is randomized into the treatment group and zero otherwise.

X – A p vector of baseline (i.e., measured prior to receiving intervention or exogenous to treatment) participant-level covariates as well as blocking variables to account for the variation in outcomes associated with these groups. These covariates, listed in detail in Table 2 in the appendix, will include:

- a) Age – age (based on date of birth) reported by agency staff or therapist at screening (continuous; range 14-19); variable will be re-centered at the grand mean for analysis.
- b) Race – race of participant as self-reported at baseline. Race will be coded as a set of $4-1 = 3$ dummy variables (each coded as 1 if they are of the specified race and coded as 0 otherwise); each of the variables will be re-centered at the grand mean for analysis.
- c) Hispanic/Latino – self-reported as Hispanic, Latino, or of Spanish origin at baseline (0=do not identify as Hispanic/Latino/Spanish origin; 1=identify as Hispanic, Latino, of Spanish origin); variable will be re-centered at the grand mean for analysis.
- d) High school education – self-reported education at baseline. A dummy variable (0= has not completed high school; 1= has completed high school); variable will be re-centered at the grand mean for analysis.
- e) State – An $n-1$ vector of state indicator dummy variables that are coded one if the intervention was delivered at state n and coded zero otherwise. State 1 is the reference category and is excluded from analysis. The dummy variables will be mean-centered for analysis to facilitate interpretation.
- f) Female – A dummy variable that is coded 1 if the participant self-reported being female at screening and coded 0 otherwise; variable will be re-centered at the grand mean for analysis.

β_0 – The intercept term, which represents, depending on the outcome measure of interest in the analysis, the outcome for the average control participant with all other variables in the model held constant at their mean.

β_1 – This is the parameter estimate of substantive interest. β_1 represents, depending on the outcome measure of interest in the analysis, either: 1) the adjusted mean difference in treatment and control participants' self-reported times having sex without condoms in the past three months at the nine-month follow-up; or 2) the adjusted mean difference in treatment and control participants' self-reported number of sexual partners in the past three months at the nine-month follow-up.

ε – The error term or unexplained individual-level variance that remains for each observation after the structural components of the model are estimated. It is the difference between the observed and the predicted values at the individual level.

We will report model-estimated effects and the results of significance tests in the findings section of the final impact report. Statistical significance will be based on test statistics produced by Stata for the coefficient β_1 using a two-tailed test, with $p < .05$.

- ii.* **Sample attrition:** Overall and differential attrition will be calculated using the full sample of participants enrolled in the study. This will be determined using data within the *Participant Database*. We will calculate overall attrition using the following formula:

$$Attrition_{participant} = 1 - \left(\frac{Assessed_{participant}}{Base_{participant}} \right)$$

where:

$Attrition_{participant}$ - the proportion of participants enrolled in the study who did not complete a 9-month follow-up questionnaire
 $Base_{participant}$ - the number of participants enrolled into the study
 $Assessed_{participant}$ - the number of participants who completed a 9-month follow-up questionnaire

Differential attrition will be calculated using the following formulas:

$$Attrition_{participant} C = 1 - \left(\frac{Assessed_{participant} C}{Base_{participant} C} \right)$$

$$Attrition_{participant} T = 1 - \left(\frac{Assessed_{participant} T}{Base_{participant} T} \right)$$

$$Differential\ Attrition_{t-c} = abs(Attrition_{participant} T - Attrition_{participant} C)$$

Where:

$Differential\ Attrition_{t-c}$ - the absolute difference between the proportion of treatment group participants who did not complete a 9-month follow-up questionnaire and the proportion of control group participants who did not complete a 9-month follow-up questionnaire
 $Attrition_{participant} C$ - the proportion of participants enrolled in the study and randomly assigned to the control group who did not complete a 9-month follow-up questionnaire

$Base_{participant} C$ - the number of participants enrolled into the study and randomly assigned to the control group
 $Assessed_{participant} C$ - the number of participants randomly assigned to the control group who completed a 9-month follow-up questionnaire

$Attrition_{participant} T$ - the proportion of participants enrolled in the study and randomly assigned to the treatment group who did not complete a 9-month follow-up questionnaire
 $Base_{participant} T$ - the number of participants enrolled into the study and randomly assigned to the treatment group
 $Assessed_{participant} T$ - the number of participants randomly assigned to the treatment group who completed a 9-month follow-up questionnaire

Overall and differential attrition will be reported in the findings section of our final impact report.

iii. **Adjustments for multiple comparisons:** Following guidance provided under the grant for our impact analysis plan⁴¹, we will adjust for multiple comparisons in all of our primary

⁴¹ During the January 8, 2019 OAH TPP Tier 2b Group Call on Impact Analysis Plans, the presenters noted that multiple comparison adjustment is required for all model-generated effect estimates of primary outcome measures.

outcome s analyses, regardless of outcome domains. We propose to use the Benjamini-Hochberg method.⁴² This method controls for the false discovery rate (FDR), which is the expected value of the number of false positive tests divided by the total number of significant tests within a family of tests. The following procedures will be used to implement this adjustment:

1. The p-values generated by our models of the effect of the intervention on our three primary outcome measures will be ranked from smallest to largest, indexed by i (where $i = 1$ for the smallest p-value and $i = k$ for the largest p-value).
2. Beginning with the largest p-value (p_{k1}), we will assess if $p_{k1} < ((i/m)a^*)$, where $m =$ the total number of tests conducted, and a^* = the initial significance value at which we would reject the null hypothesis and the level of false discovery we are willing to accept (in this case, 0.05). The null hypothesis will be rejected and the test will be considered statistically significant if $p_{k1} < ((i/m)a^*)$. If $p_{k1} < ((i/m)a^*)$, all smaller p-values in the list will also be considered statistically significant and the null hypothesis will be rejected for each test. If $p_{k1} \geq ((i/m)a^*)$, the null hypothesis will hold, the test will not be considered statistically significant, and the next largest p-value in the ranked list will be assessed.
3. If the 1st p-value is not statistically significant, the 2nd largest p-value in the list (p_{k2}) will be compared against $(i/m)a^*$. The null hypothesis will be rejected and the test will be considered statistically significant if $p_{k2} < ((i/m)a^*)$. If $p_{k2} < ((i/m)a^*)$, all smaller p-values in the list will also be considered statistically significant and the null hypothesis will be rejected for each test. If $p_{k2} \geq ((i/m)a^*)$, the null hypothesis will hold, the test will not be considered statistically significant, and the next largest p-value in the ranked list will be assessed.
4. If the 2nd p-value is not statistically significant, the 3rd largest p-value in the list (p_{k3}) will be compared against $(i/m)a^*$. The null hypothesis will be rejected and the test will be considered statistically significant if $p_{k3} < ((i/m)a^*)$. If $p_{k3} \geq ((i/m)a^*)$, the null hypothesis will hold and the test will not be considered statistically significant.

iii. **Sensitivity analyses:** We will conduct sensitivity analyses to test the robustness and validity of our benchmark approaches outlined above. These include: (1) excluding covariates; (2) not adjusting for missing baseline data; (3) excluding unreliable data; (4) excluding outliers; (5) condensing data collection windows to exclude late responders; and (6) estimating an empirical model that uses appropriate alternative approach if analytic sample size is not sufficient for benchmark approach.

1. **Without baseline covariates.** Our benchmark approach is to include baseline covariates in our model to improve the precision of our estimates. To test this, we will conduct sensitivity analyses that involve running identical empirical models without the covariates included. Analytic findings for both approaches will be presented alongside each other in an appendix of the impact report.
2. **Without adjusted baseline data.** As outlined in the *Missing data approach section*, our benchmark approach is to adjust baseline data as published guidance suggests that this may produce unbiased impact estimates and maximize the use of available data. We will test this by way of sensitivity analyses that involve running identical empirical models without the adjusted data. Analytic findings for both approaches will be presented alongside each other in an appendix of the impact report.

⁴² This method has been selected because it helps to control the Type 1 error rate without also increasing the Type 2 error rate, which in our view is a serious consideration in preliminary efforts to identify evidence of effectiveness of new approaches. Benjamini, Y., & Hochberg, Y. (1995). Controlling the false discovery rate: a practical and powerful approach to multiple testing. *Journal of the royal statistical society. Series B (Methodological)*, 289-300.

As outlined in the *Baseline equivalency* section, we will also produce diagnostic estimates of baseline equivalency on the pre-intervention outcome variables according to our benchmark approach and the sensitivity study alongside each other in an appendix of the report.

3. **With unreliable data.** As discussed in the *Data cleaning* section, data for cases that are deemed unreliable are treated as *unit missing* and excluded from benchmark analyses. To test this, we will conduct sensitivity analyses that involve running identical empirical models with the unreliable data included. Analytic findings for both approaches will be presented alongside each other in an appendix of the impact report.
4. **Without outliers.** As discussed in the *Data cleaning* section, extreme data values are investigated and flagged as outliers. Our benchmark analytic approach is to include data flagged as outliers (i.e., extreme values that are not considered invalid) in analysis. We will also conduct sensitivity analyses that exclude these data and report substantive differences in the results section of the report.
5. **Condensed data collection windows.** Our benchmark approach is to include follow-up data from all participants who completed a questionnaire during their open data collection window, regardless of the time point in that window when it was completed. Data collection windows are broad to minimize attrition from the analytic sample. To examine whether or not this influences our results – and, in particular, whether or not study participants who respond later report different outcomes from those who respond earlier – we will conduct an analysis that examines the difference, if any, in response time between treatment and control participants and compares impact estimates for analytic samples without late responders. Late responders will be defined as those participants who complete their nine-month questionnaire more than one month after the initiation of the nine-month data collection window.
6. **Using alternate model specification.** Our benchmark approach is to use OLS regression to estimate the effects of the intervention on each of our primary outcomes of interest. This approach is deemed appropriate even in the instance the dependent variable is not normally distributed – as may be the case with our outcomes – so long as the sample size is sufficiently large.⁴³ In the instance our analytic sample size does not reach 500 participants (the threshold at which we consider a sample large), we propose to conduct diagnostic tests to identify an appropriate alternative estimation approach (e.g., transformation of the dependent variable, Bayesian approach, non-parametric model) that will be used to conduct sensitivity analyses to test the robustness of our results.

5. **Additional planned analyses:** We intend to investigate the following exploratory research questions in addition to the primary research questions described above.

Antecedents of Sexual Behavior

- a. What are the short-term (post-program) and long-term (nine-month follow-up) impacts of the offer to participate in *PS-R* (treatment) relative to the offer to participate in *TPG* (comparison) on the following antecedents of participants' sexual behavior:
 - i. Perception of risk and severity for pregnancy and HIV/STIs

⁴³ Lumley, T., Diehr, P., Emerson, S., Chen, L. (2002). The Importance of the Normality Assumption in Large Public Health Datasets. *Annual Review of Public Health*. 23:151–69
DOI: 10.1146/annurev.publhealth.23.100901.140546

- ii. Intention to have sex
- iii. Importance of having sex
- iv. Intention to use effective contraceptive methods (including condoms)
- v. Importance of using effective contraceptive methods
- vi. Intention to limit number of sexual partners
- vii. Importance to limiting the number of sexual partners
- viii. Intention to practice affect regulation
- ix. Importance of using affect regulation
- x. Intention to practice sexual self-regulation
- xi. Importance of practicing sexual self-regulation
- xii. Contraceptive use and negotiation (including condoms) self-efficacy
- xiii. Sexual activity decision making and planning self-efficacy
- xiv. Beliefs regarding malleability of emotions
- xv. Beliefs regarding value of affect regulation
- xvi. Affect regulation self-efficacy
- xvii. Use of affect regulation
- xviii. Self-esteem
- xix. Distress

Primary Outcomes Measured at Short-term Follow-up

- a. What are the short-term (post-program) impacts of the offer to participate in *PS-R* (treatment) relative to the offer to participate in *TPG* (comparison) on the primary outcomes of interest:
 - i. Number of times having sex without a condom
 - ii. Number of sexual partners

Other Sexual Behaviors and Sexual Health Outcomes

- a. What are the short-term (post-program) and long-term (nine-month follow-up) impacts of the offer to participate in *PS-R* (treatment) relative to the offer to participate in *TPG* (comparison) on the following sexual behaviors:
 - i. Number of times having sex without any protection (prescription birth control or condoms)
 - ii. Number of times having sex using dual methods of protection (prescription birth control and condoms)
- b. What are the long-term (nine-month follow-up) impacts of the offer to participate in *PS-R* (treatment) relative to the offer to participate in *TPG* (comparison) on the following pregnancy outcomes
 - i. Ever being pregnant?
 - ii. Times being pregnant?

Effects of Mediators on Primary Outcomes of Interest

- a. What are the short-term (post-program) and long-term (nine-month follow-up) impacts of the offer to participate in *PS-R* (treatment) relative to the offer to participate in *TPG* (comparison) on participants' reported times having sex without condoms considering the following potential mediators:
 - i. Perception of risk and severity for pregnancy and HIV/STIs
 - ii. Intention to have sex
 - iii. Importance of having sex
 - iv. Intention to use effective contraceptive methods (including condoms)
 - v. Importance of using effective contraceptive methods
 - vi. Intention to limit number of sexual partners
 - vii. Importance to limiting the number of sexual partners
 - viii. Intention to practice affect regulation

- ix. Importance of using affect regulation
- x. Intention to practice sexual self-regulation
- xi. Importance of practicing sexual self-regulation
- xii. Contraceptive use and negotiation (including condoms) self-efficacy
- xiii. Sexual activity decision making and planning self-efficacy
- xiv. Beliefs regarding malleability of emotions
- xv. Beliefs regarding value of affect regulation
- xvi. Affect regulation self-efficacy
- xvii. Use of affect regulation
- xviii. Self-esteem
- xix. Distress

b. What are the short-term (post-program) and long-term (nine-month follow-up) impacts of the offer to participate in *PS-R* (treatment) relative to the offer to participate in *TPG* (comparison) on participants' reported number of sexual partners considering the following potential mediators:

- i. Perception of risk and severity for pregnancy and HIV/STIs
- ii. Intention to have sex
- iii. Importance of having sex
- iv. Intention to use effective contraceptive methods (including condoms)
- v. Importance of using effective contraceptive methods
- vi. Intention to limit number of sexual partners
- vii. Importance to limiting the number of sexual partners
- viii. Intention to practice affect regulation
- ix. Importance of using affect regulation
- x. Intention to practice sexual self-regulation
- xi. Importance of practicing sexual self-regulation
- xii. Contraceptive use and negotiation (including condoms) self-efficacy
- xiii. Sexual activity decision making and planning self-efficacy
- xiv. Beliefs regarding malleability of emotions
- xv. Beliefs regarding value of affect regulation
- xvi. Affect regulation self-efficacy
- xvii. Use of affect regulation
- xviii. Self-esteem
- xix. Distress

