- Second, we create an outlier indicator variable, where observations deemed severe outliers are coded as 1, all others are coded as 0.

Our benchmark analytic approach is to include data flagged as outliers in analysis, because we do not know for certain whether the values are true or invalid. However, we also run sensitivity analyses that exclude these data and report substantive differences in the results section of the report.

iv. **Identify and flag inconsistencies in reporting of sexual behaviors:** The fourth step in the data review process is to inspect the data and identify inconsistencies in sexual behavior outcome data. With repeated measures of sexual behaviors, two primary types of inconsistencies may occur – internal inconsistencies and over-time inconsistencies.²⁴ Internal inconsistencies refer to discrepancies in responses (to related questions) in the same survey administration. For instance, a respondent might say that they have not had sex in the past three months, but then indicates that they used condoms three of the times they had sex in the past three months. Over-time inconsistencies refer to instances in which lifetime reported behaviors decline or are completely recanted over time. For example, at baseline a respondent might say that they have had vaginal sex in their life, but on a subsequent administration of the survey say that they have never had vaginal sex.

In order to minimize internal inconsistencies in our primary outcomes, we built skip patterns into the online questionnaire – if participants indicate they have not had a particular type of sex they are skipped out of more specific questions related to that type of sex; and if they state they have never had sexual contact, they are then skipped out of questions asking about how many sexual partners they have had over certain periods of time. In addition, participants are precluded from indicating they had a particular type of sex without a condom more times than they said they had that type of sex. Because of this, no internal inconsistencies can exist in our primary outcome measures.²⁵

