To address over-time inconsistencies, a research analyst examines all variables that are used to construct primary outcome measures, as well as any variables that may be used to logically impute values for primary outcome measures. If over-time inconsistencies are identified, both the baseline and follow-up values are flagged as inconsistent over time and recoded to missing (coded as “.k.”). Data that are recoded to missing are treated according to our missing data approach. Briefly, our benchmark approach is to adjust

²⁴ Inconsistencies can occur for a number of reasons including social desirability bias and memory or recall issues on the part of the respondent and misunderstanding on the part of either the respondent or interviewer (Alexander et al 1993; Clarke, Fiebig, and Gerdtham 2008; Del Boca and Noll 2000; Harris et al 2008; Schroeder et al 2003; Schwarz and Oyserman 2001). These issues are especially common in self-reports of sexual behaviors where questions are of a sensitive nature and often respondents are asked to indicate the frequency and/or recency of behaviors over differing lengths of time (e.g., 30 days, 3 months, 6 months).

²⁵ In rare instances, paper-based questionnaires are completed by participants. This may occur if the study coordinator is unable to open the online questionnaire because of network connection issues, or if the participant cannot be reached for an online administration and is instead mailed a paper questionnaire. Paper-based questionnaires include the same skip patterns as online questionnaires; however, unlike the online questionnaire where participants are skipped out of subsequent questions based on their response to previous questions and cannot report inconsistent times having different types of sex or number of sexual partners, it is possible for participants to provide responses to questions that they should not have answered or that do not make sense given their responses to previous questions. If and when such inconsistencies are observed in data originating from paper-based questionnaires, the participant's responses to the two or more items where inconsistencies are noted are recoded to system missing and will not be used in our primary outcome analysis.

missing baseline data and include in analysis; we exclude observations with missing outcome data from analysis.

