3. Determine if logical imputations are possible for any analytic variables that may have missing values (due to nonresponse) and logically impute where this is the case. We will not logically impute where the missing values are previously inconsistent, unreliable, or invalid.
4. Determine if any individuals who are in the randomized sample (for each outcome) do not have outcome data at the nine-month follow-up time point. If this is the case, our proposed benchmark approach is to use case deletion, as we feel it is the most straightforward and prudent approach for missing follow-up data

²⁶ Puma, M.J., Olsen, R.B., Bell, S.H., Price, C. (2009). What to Do When Data Are Missing in Group Randomized Controlled Trials. (NCEE 2009-0049). Washington, DC: National Center for Education Evaluation and Regional Assistance, Institute of Education Sciences, U.S. Department of Education. Moher, D. et al. (2010). CONSORT 2010 Explanation and Elaboration: Updated Guidelines for Reporting Parallel Group Randomised Trials. *BMJ* 2010;340:c869.

²⁷ We will code missing responses with a unique missing code that identifies or flags these missing values according to the reason they are missing (i.e., nonresponse, invalid, inconsistent). Unreliable data are not recoded to missing, rather cases deemed unreliable are coded as 1 in an indicator variable, treated as unit missing, and excluded from analysis. See the *Data cleaning* section or Table 3 in the Appendix for details on how missing data are coded.

²⁸ For item missing values, we will only report prevalence of missing and inconsistent data for variables that are included in our model specifications and could therefore influence the constitution of the analytic sample.

recommended in Puma et al. (2009). These cases will be deleted from the analytic sample and attrition statistics will be reported.

5. Determine if any individuals who are in the randomized sample (for each outcome) are missing baseline covariates or the baseline measure of the outcome variable. If this is the case, our proposed benchmark approach is to use dummy variable adjustment procedures, as we feel it is the most straightforward and prudent approach for missing baseline/covariate data recommended in Puma et al. (2009).

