We propose to assess baseline equivalence of the treatment and control groups according to a multi-step procedure. Baseline equivalence statistics will be produced for each analytic sample.³² Only participants who provide baseline data to an outcome measure will be included in the analytic sample for that same outcome measure; thus the analytic sample used for each research question may vary slightly because of the exclusion of non-responders. As required by the “Identifying Programs that Impact Teen Pregnancy, Sexually Transmitted Infections, and Associated Sexual Risk Behaviors” review protocol, we will report the adjusted means and p-values of the differences in the baseline variable of interest for the treatment and control groups.³³ We will also report the standardized mean difference of each baseline variable for the treatment and control groups. This last statistic is not required by the review protocol but it is more consistent with the literature on balance statistics.³⁴

To establish baseline equivalence, we propose to generate model-based point estimates of the difference between the treatment and control groups for the identified baseline equivalence variables. We will report the adjusted means and p-values of the differences in the baseline variable of interest for the treatment and control groups. We will then compute the pooled standard deviation of these variables. Finally, we will produce a standardized difference of means by dividing the first term by the second.³⁵

step 1. First, we generate a model-based estimate of the difference between treatment and comparison groups on the pre-intervention measures identified above. Separate models will be run for each of the variables. The empirical model will be estimated with OLS (using Stata). If the measure is dichotomous, we propose to use a linear probability model to estimate the predicted probability of group membership. The model is a reduced-form variation of the model that we use to estimate program impact (as detailed in the *Model specification and covariates* section, below).³⁶

$$Y_{baseline} = \beta_0 + \beta_1 T + \sum (\beta_p X_p) + \varepsilon$$

where:

³² Due to item missing outcome data, we expect there may be slight differences in analytic samples for each research question.

³³ Goesling, B., & Trenholm, C. (2016). Identifying Programs that Impact Teen Pregnancy, Sexually Transmitted Infections, and Associated Sexual Risk Behaviors. Mathematica Policy Research.

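### Recanted nine-month reports appear to be deleted from the primary outcomes, but the attrition formulas omit them and no sensitivity analysis covers them (minor, inexpensive to fix)

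*Combined protocol and SAP*

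**What the plan says.** - **Definition.** Section 4c.iv: "Over-time inconsistencies refer to instances in which lifetime reported behaviors decline or are completely recanted over time".
- **Handling.** The same section provides that "both the baseline and follow-up values are flagged as inconsistent over time and recoded to missing", with code .k, and that "we exclude observations with missing outcome data from analysis".
- **No repair.** Section 4c.v, step 3: "We will not logically impute where the missing values are previously inconsistent, unreliable, or invalid".
- **Deletion.** Step 4 works outcome by outcome on participants without nine-month data: "These cases will be deleted from the analytic sample and attrition statistics will be reported".
- **Outcome coding.** Section 4a codes a youth with no lifetime sexual contact as having zero partners. The condom outcome sums three items (vaginal, oral, anal), and a type of sex never had counts as zero.
- **Attrition.** Section 4f.ii defines the assessed count, overall and by arm, as participants who completed a nine-month questionnaire.
- **Robustness checks.** Section 4f lists six sensitivity analyses. Section 3d adds one excluding phone respondents, and footnote 40 adds a logistic model.
- **Text pointing the other way.** The Table 1 notes put every respondent with nine-month data in the analytic sample and count no sexual contact as zero partners. For .k items, Table 3 mentions only adjustment of baseline values.

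**The concern.** Whether a youth enters the primary partners analysis depends partly on an answer given after randomization about the behavior the intervention targets. Two gaps follow.

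First, the attrition figures will not register these losses. Step 4 of Section 4c.v promises attrition statistics for deleted cases, and footnote 39 makes unbiasedness conditional on low overall and differential attrition. A formula based on questionnaire completion gives one figure for both outcomes and counts a deleted youth as assessed.

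Second, no planned analysis shows whether the estimate depends on the deletion. The plan keeps outliers and also tests excluding them; it excludes unreliable cases and also tests including them. Inconsistent outcomes get no such check, although a recanted report is just as uncertain.

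**Working it through.** **Tracing one respondent.** A youth reports sexual contact at baseline and none ever at nine months.

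1. Section 4a alone would code zero partners.
2. Section 4c.iv treats the report as recanted and sets both values to .k.
3. Section 4c.v, step 3, prevents the zero from being restored by logical imputation.
4. Step 4 deletes the case from the partners model.
5. Section 4f.ii still counts the youth as assessed.

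For the condom outcome, recanting one type of sex makes one of three items .k. If all three items are needed, the youth is deleted, possibly with a positive total on the others. If available items are summed, the youth stays. The plan does not say which.

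None of the planned checks restores these outcomes. The run without adjusted baseline data only removes further cases, and unreliable refers to patterned answering.

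**Attrition.** The documents give no completion or recanting rate, so both are assumed. Inputs: 400 enrolled (study changes timeline, November 2018), 1:1 allocation, so 200 per arm; 80% completion, so 160 completers per arm; r = share of completers flagged.

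- Plan's formula: 1 − 320/400 = 20%; differential |20% − 20%| = 0 points, whatever r is.
- Loss on participants analysed: 1 − 0.8(1 − r) per arm.

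| r, the two arms | Analysed per arm | Overall loss | Differential |
|---|---|---|---|
| 2%, 2% | 156.8, 156.8 | 1 − 313.6/400 = 21.6% | 0 points |
| 2%, 4% | 156.8, 153.6 | 1 − 310.4/400 = 22.4% | 3.2/200 = 1.6 points |
| 5%, 10% | 152, 144 | 1 − 296/400 = 26.0% | 8/200 = 4.0 points |

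At 70% or 90% completion, the uncounted differential in the last row is 3.5 or 4.5 points.

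**Effect on the partners estimate, no true effect.** The answer depends on what the flagged youths' true values are.

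- *Flagged youths truly average their arm mean.* Deletion causes no bias.
- *Deleted values are true zeros.* The retained mean is μ/(1 − r). Equal r gives a ratio of 1. At 2% versus 4% the ratio is 0.98/0.96 = 1.021. At 5% versus 10% it is 0.95/0.90 = 1.056, or 0.947 reversed.

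For the 5% versus 10% case, assume an SD of 1.2 to 2.0 times the mean. The false difference is μ(1/0.90 − 1/0.95) = 0.0585μ. The standard error is SD × √(1/152 + 1/144), that is 0.1395μ to 0.2326μ. The shift is 0.42 to 0.25 standard errors, and two-sided rejection at 0.05 is 7.0% to 5.7% (normal approximation). At 2% versus 4% it is 5.1% to 5.3%.

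Those rates precede the Benjamini-Hochberg step that Section 4f.iii requires. With the two listed primary outcomes, only partners shifted, and correlation between the test statistics from 0 to 0.9, simulation gives partners rejection of about 3.1% to 4.6% at 5% versus 10%. With no shift it is about 2.6% to 3.6%.

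**The case against.** **Treating both answers as missing is defensible.** At least one of the two answers is false. Online, a youth who answers never skips the three-month question (footnote 15), so the zero is a skip code and not an observed count. Keeping it can itself mislead: if flagged youths truly average their arm mean, retaining zeros at 10% versus 5% makes the more-flagged arm look 1 − 0.90/0.95 = 5.3% lower. This stands, and is why the benchmark should not change.

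**Much is already disclosed.** Footnote 19 and step 2 of Section 4c.v commit to inconsistency counts by arm, and footnote 35 puts baseline equivalence on the exact analytic sample. These make the deletions visible. They do not show whether the estimate moves, and balance tables compare measured baseline variables only. The attrition formulas still give a different figure from the loss at analysis.

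**Deletion is not certain.** Tables 1 and 3 can be read as keeping these youths. The explicit rules in Sections 4c.iv and 4c.v support deletion, but the conflict is real and is part of this point.

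**Stronger readings that the documents do not support.** A reader might infer that the trial expects frequent recanting, since footnote 24 says "These issues are especially common in self-reports of sexual behaviors where questions are of a sensitive nature". That sentence concerns the causes of inconsistent reporting in general, and Section 4c.iv is conditional on inconsistencies being found. Footnote 18 expects data to be either wholly missing or present, and footnote 32 expects at most slight differences between samples. A reader might also infer that the primary result is biased or its error rate materially inflated. Nothing shows that flagging differs by arm, both arms get the same questionnaire, and the planned multiplicity adjustment lowers the rejection rates. Footnote 39 sets no numeric attrition threshold, so none is shown to be crossed.

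**Conclusion.** The point holds as a minor one. Under the plan's own deletion rule, the attrition formulas understate outcome-specific loss even when the arms are flagged equally: 20% reported against 21.6% at the assumed 80% completion and 2% flagging. The differential is understated only if flagging differs by arm.

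Bias in the treatment estimate is unknown in size and direction and probably small. It is nil with equal flagging, or if flagged youths truly average their arm mean. It is about 5% of the mean if deleted values are true zeros and the arms differ 5% versus 10%, with partners rejection of about 5.7% to 7% before Benjamini-Hochberg and about 3% to 4.6% after it when only partners is shifted. All completion rates, flagging rates and SDs here are assumptions. For the condom outcome, deletion is possible but depends on an unstated rule.

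**What to change.** 1. Report overall and differential attrition separately for each primary outcome, with the assessed count equal to participants actually analysed, beside the questionnaire-completion figures.
2. Keep the benchmark. Add one robustness run per primary outcome that retains flagged nine-month outcomes as coded under Section 4a and handles the inconsistent baseline value by the planned dummy-variable adjustment. State that a retained zero is a skip code that may be false, so a difference between runs shows sensitivity and not which run is right.
3. Reconcile Tables 1 and 3 with Sections 4c.iv and 4c.v. Also reconcile step 5 of Section 4c.v, which keeps participants who "are missing baseline covariates or the baseline measure of the outcome variable", with Section 4d, which says: "Only participants who provide baseline data to an outcome measure will be included in the analytic sample for that same outcome measure". Read literally, the latter would drop the retained youths again.
4. State how the condom sum is formed when one item is .k.

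The cost is one extra model run per primary outcome, the per-outcome attrition lines and a few sentences. No new data are needed.
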